The goal of the proposed trial is to experimentally model whether increasing the availability and appeal of an alternative, non-combusted source of nicotine (e-cigarettes) enhances the effects of reduced-nicotine cigarettes in smokers with ADs. Daily smokers with current ADs, recruited at University of Vermont and Brown University, will be randomized to one of the following four conditions: (1) normal nicotine content cigarettes (NNCCs) alone, serving as the control condition, (2) VLNCCs alone, (3) VLNCCs + nicotine e-cigarettes in only tobacco flavors (TF e-cigs), or (4) VLNCCs + nicotine e-cigarettes in preferred flavors (PF e-cigs). Participants will be asked to use only their assigned study products for 16 weeks. Outcome measures include total CPD, cigarette demand assessed by behavioral economics-based purchase tasks, craving, withdrawal, psychiatric symptoms, breath carbon monoxide (CO) and biomarkers of tobacco toxicant exposure. In Week 17, participants will receive incentives to abstain from cigarettes during a three-hour laboratory test session and we will assess the effects of study conditions on cigarette demand, craving and withdrawal.

This research will address the following specific aims: Aim 1 (Primary): Compare the effects of (1) NNCCs alone, (2) VLNCCs alone, (3) VLNCCs + TF e-cigs and = (4) VLNCCs + PF e-cigs on total CPD in smokers with ADs. We hypothesize that at Week 16, total CPD will be reduced in a linear, graded manner (condition 4 > 3 > 2 > 1), with the largest reduction in the VLNCC + PF e-cig condition. Aim 2 (Secondary): Compare the effects of the four study conditions on cigarette demand, psychiatric symptoms, and biomarkers of smoke and tobacco toxicant exposure (CO, NNAL, PAHs) in smokers with ADs. We hypothesize that at Week 16, cigarette demand, CO, and toxicant biomarkers will have decreased in a linear, graded manner, with the largest reduction in the VLNCC + PF e-cig condition. We will characterize effects on psychiatric symptoms but are not testing specific hypotheses on these symptoms. Aim 3 (Exploratory): To explore the effects of the four study conditions on cigarette demand, craving, and withdrawal in smokers with ADs during the abstinence assessment period.

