After the week 16 visit, participants will be required to attend one additional visit the following day. During this visit, participants will have been encouraged to abstain from smoking until their next scheduled visit (approximately 24 hours later). The abstinence assessment session should be scheduled no less than 18 hours and no more than 30 hours after the Week 16 visit. Abstinence will be verified by an expired breath carbon monoxide level of less than or equal to 6 parts per million (ppm). This session will allow us to determine whether the experimental cigarettes and e-cigarette use (for the e-cigarette conditions) have reduced the effects of abstinence on these measures relative to the control conditions. If the participant does NOT meet abstinence criteria, he/she will only receive \$20 for the visit. Those who do meet abstinence criterion will do concurrent choice session

detailed below.

7.8.A Participants Who Meet Criteria for Abstinence

7.8.A.1 Measures/Assessments

Physiological measures collected and entered directly into REDCap by the interviewer at the end of the visit:

- 1) CO
- 2) Blood Pressure
- 3) Heart Rate
- 4) Body temperature
- 5) Oxygen saturation
- 6) Respiratory rate
- 7) Urine or Saliva Toxicology

The following assessments will be administered as an interview and will be entered directly into REDCap by the interviewer:

- 1) Concomitant Medications
- 2) Medical Event Form, if applicable
- 3) Health Changes Questionnaire
- 4) Time Since Last Cigarette Questionnaire

The following assessments will be completed by the participant directly in REDCap:

- 1) BDI
- 2) OASIS
- 3) COVID19 Symptom Questionnaire
- 4) Respiratory Symptom Questionnaire
- 5) MNWS
- 6) PANAS
- 7) QSU-brief - Usual Cigarette
- 8) QSU-brief - Study Cigarette
- 9) Vaping Craving Questionnaire
- 10) Cigarette Purchase Task - Usual Brand Cigarette Version
- 11) Cigarette Purchase Task - Study Cigarette Version
- 12) E-cigarette Purchase Task- E-cigarette Version
- 13) Snaith-Hamilton Pleasure Scale (SHAPS)

In the event that the REDCap website is not functioning, the assessments will be administered aloud and participant answers will be recorded securely. The interviewer will enter the data into REDCap when it resumes functioning properly. This information should be recorded in the 'End of Visit Evaluation Form'.

7.8.B. Participants Who Do Not Meet Criteria for Abstinence

7.8.B.1 Measures/Assessments

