Participants who do NOT meet abstinence criteria will be required to complete the following assessments:

- 1) CO
- 2) Blood Pressure
- 3) Heart Rate
- 4) Body temperature
- 5) Oxygen saturation
- 6) Respiratory rate
- 7) Urine or Saliva Toxicology

The following assessments will be administered as an interview and entered directly into REDCap by the interviewer:

- 1) Concomitant Medications
- 2) Health Changes Questionnaire
- 3) Medical Event Form, if applicable
- 4) TLFB

The following assessments will be completed by the participant directly in REDCap:

- 1) BDI
- 2) OASIS
- 3) COVID19 Symptom Questionnaire
- 4) Respiratory Symptom Questionnaire

7.9. Participant Compensation:

Participants will receive \$25 plus a \$25 bonus for completing each screening visit on time as scheduled. Payment for the first screening session will be made upon its completion. Payment for the second screening session will be made regardless of enrollment as long as the participant passes the drug test and meets the minimum requirements for carbon monoxide or urinary cotinine levels. Participants who do not pass the drug test or who are visibly intoxicated as determined by slurred speech, swaying, or stumbling-will not be able to complete the visit and will be asked to take another test several days after the first positive. If they are negative for the second test, they will be eligible to participate, and if they are positive for the second test they will be excluded. Participants will receive \$100 for each study visit from Baseline 1 to Week 16. Participants will also have a chance to earn an additional \$20 bonus for every study visit that is completed on time as scheduled starting at Week 1 and ending at Week 15.

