9.1 Statistical Methods

Continuous outcomes will be summarized by mean, standard deviation, median and range. Categorical outcomes will be summarized by frequencies and percentages. Skewed continuous outcomes will be log- or square-root transformed as appropriate. Variables measured at each baseline visit will be averaged and the average will be used as the baseline measurement. As we expect conditions to be balanced on important baseline characteristics due to randomization, our primary analysis for all endpoints will not be adjusted for potential confounders. However, a secondary analysis will be completed for all outcomes adjusting for demographic characteristics (e.g., age), that we have found to be important in prior studies. Potential moderators (e.g., SSRI vs. non-SSRI antidepressant, depression vs. anxiety disorders, BMI above or below 30) will be explored by adding that term and the moderator-by-condition term to the model. We will examine age group and gender as potential moderators in a similar fashion.

Participants will be randomized in equal probability to one of the four conditions, with randomization stratified by site and menthol cigarette status. All analyses will follow the intent-to-treat principle (i.e. subjects will be analyzed according to condition assignment, regardless of compliance). The Primary Aim will examine the effects of condition on total CPD (study product and non-study product). CPD will be analyzed by week (mean over all days in a seven-day period) using a mixed model to account for repeated measures from the same individual.

Models will include baseline CPD as a covariate. Using a mixed model also allows us to include the effect of study site as a random effect. Additional analyses conducted using data collected at the end of the study will use orthogonal comparisons to test for a linear trend in the decrease in CPD, such that VLNCC + PF e-cig > VLNCC + TO e-cig > VLNCC > NNCC, with

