the largest reduction in the VLNCC + PF e-cig condition. As we expect that differences among conditions for some of the outcomes may not follow a linear pattern, we will use related planned comparisons to test for threshold effects, specifically contrasting the NNCC condition to all three VLNCC conditions, and NNCC to the two VLNCC + e-cigarette conditions.. Analysis of cigarette demand, smoke exposure and tobacco carcinogens (Aim 2) as well as additional outcomes, including subjective effects, will be analyzed in a similar manner. Because Exploratory Aim 3 is based on abstinence-induced effects and will be examined using data collected at a single visit at Week 17, analysis will be based on an analysis of co-variance model. In addition to the effect of condition, we will include important covariates noted above. Exploratory analyses will also be conducted combining data collected from three of the vulnerable populations (disadvantaged women of childbearing age, opioid dependent individuals, individuals with AD) to explore potential differences in effects of study condition across these populations. This will be done with the addition of the effects of population and population-by-condition terms to the models described above. Study staff will make every effort to minimize missing data, and results of our ongoing trial suggest that this will be minimal. We will examine the missing data pattern, and if it is missing at random, will use all data available, without imputation.

permutation tests.¹²¹

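### Aim 3 craving, withdrawal and demand are collected only from participants who pass the CO check, so the conditions are compared in a post-randomisation subset that section 9.1 does not declare as an exception to ITT

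*Combined protocol and SAP*

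**What the plan says.** Section 1 states Aim 3 as "To explore the effects of the four study conditions on cigarette demand, craving, and withdrawal in smokers with ADs during the abstinence assessment period". The gate is in section 7.8: "Abstinence will be verified by an expired breath carbon monoxide level of less than or equal to 6 parts per million (ppm", at a visit 18 to 30 hours after the Week 16 visit.

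What is collected then depends on the result.

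- **Section 7.8.A (pass):** the REDCap list includes the MNWS for withdrawal, the QSU-brief in two versions (for example "QSU-brief - Usual Cigarette") for craving, and the purchase tasks (for example "Cigarette Purchase Task - Study Cigarette Version") for demand. The PANAS, SHAPS and Vaping Craving Questionnaire are also there.
- **Section 7.8.B (fail):** "Participants who do NOT meet abstinence criteria will be required to complete the following assessments". The list has physiological measures, toxicology, medication, health-change and medical-event forms, TLFB, BDI, OASIS, and the COVID19 and respiratory symptom forms. It has no MNWS, QSU or purchase task.

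On analysis, section 9.1 says "All analyses will follow the intent-to-treat principle (i.e. subjects will be analyzed according to condition assignment, regardless of compliance". For Aim 3, "analysis will be based on an analysis of co-variance model", with condition and covariates. Section 9.1 names no abstainer-only population and no method for participants who fail the check. Its only missing-data rule is to use available data without imputation if the pattern is missing at random.

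**The concern.** Randomisation makes the four conditions comparable among everyone assigned, not among those who later pass a biochemical check. The check is a CO threshold, and section 1 hypothesises that CO will have fallen in a graded way across conditions by Week 16. If pass rates differ by condition, passers in one arm are a more selected group than passers in another, and the ANCOVA can show or hide a difference that the products did not cause.

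The plan also contradicts itself. The by-assignment analysis promised for all outcomes cannot be run for Aim 3, because the outcome does not exist for those who fail. The missing-data rule does not resolve this. No outcome is observed above 6 ppm at this session, so a model for the missing values would have to extrapolate. Adjusting for session CO would condition on a variable that the conditions are expected to change.

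**Working it through.** **1. The lists side by side**

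| Aim 3 outcome | Instrument | 7.8.A (pass) | 7.8.B (fail) | Week 16 (7.3.A) |
|---|---|---|---|---|
| Withdrawal | MNWS | yes | no | yes |
| Craving | QSU, usual and study cigarette | yes | no | yes |
| Demand | Cigarette Purchase Task, usual and study | yes | no | yes |

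This part needs no assumption.

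**2. The plan's own sample size (section 9.2)**

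Inputs: effect size 0.60, two-sided alpha 0.05, power 80%, loss to follow-up 15%. A two-sample t-test needs 44.6, so 45 per arm, and 45 / (1 - 0.15) = 52.9, so 53. The stated figure is reproduced. It belongs to Aim 1; no power or expected pass rate is given for Aim 3.

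**3. Size of the selection effect (illustrative)**

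Model: a standardised outcome with no true condition effect, correlated rho with the tendency to fail the check. Among passers the mean is -rho × λ(p), where p is the pass rate and λ(p) = φ(z_p)/p. The spurious difference between two arms is rho × [λ(p1) - λ(p2)]. Pass rates and rho are assumptions.

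λ(0.30) = 1.159; λ(0.50) = 0.798; λ(0.60) = 0.644; λ(0.70) = 0.497; λ(0.80) = 0.350; λ(0.90) = 0.195.

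| NNCC vs e-cigarette pass rate | Difference in λ | rho 0.3 | rho 0.5 |
|---|---|---|---|
| 50% vs 60% | 0.154 | 0.05 SD | 0.08 SD |
| 50% vs 70% | 0.301 | 0.09 SD | 0.15 SD |
| 30% vs 60% | 0.515 | 0.15 SD | 0.26 SD |
| 30% vs 70% | 0.662 | 0.20 SD | 0.33 SD |
| 80% vs 90% | 0.155 | 0.05 SD | 0.08 SD |
| equal | 0 | 0 | 0 |

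For 30-50% against 60-70%, the range is 0.05 to 0.33 SD. At 30% vs 70%, a nominal 5% test would reject in about 10% (rho 0.3) to 20% (rho 0.5) of trials with no true effect. In this model the arm with more passers looks worse on craving, because its passers are less selected, so a real e-cigarette benefit could be masked.

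**4. Precision (illustrative)**

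Take 45 attendees per arm (53 less 15%) and multiply by an assumed pass rate.

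| Pass rates | Analysed per arm | Power at d = 0.60 | Effect detectable with 80% power |
|---|---|---|---|
| all attendees | 45 | 80% | 0.60 |
| 70% in both | about 31 | 65% | 0.72 |
| 50% in both | about 22 | 50% | 0.85 |
| 30% in both | about 13 | 32% | 1.12 |
| 30% vs 60% | about 13 and 27 | 42% | 0.96 |

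**The case against.** The strongest reply is that Aim 3 concerns abstinence-induced effects. Craving in someone who has just smoked is not abstinence craving, so restricting to verified abstainers may be the intended question, and an all-attendee analysis would answer another one. This stands as far as it goes. A reader might infer that the abstinent-only comparison is invalid and should be replaced; the documents do not support that. They do require that it be declared, because section 9.1 states its ITT rule without exception.

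Second, a reader might infer that passing is known to depend on condition, or that less dependent smokers are known to pass under NNCC. The documents show neither. The graded-CO hypothesis makes dependence plausible, no more. Passers also receive $120 and others $20 (section 7.9), which could make pass rates high and similar. At 80% vs 90% the effect would be 0.05 to 0.08 SD.

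Third, a reader might infer that nothing could be done about the selection afterwards. That goes too far. The Week 16 schedule gives the MNWS, QSU and both Cigarette Purchase Tasks to all participants about a day earlier, and those who fail still supply CO and TLFB. Pass rates can be reported, and weighting or adjustment on Week 16 values is possible. The planned covariates may also remove some of the selection, which the unadjusted formula ignores. What stays lost is the abstinence-session value itself.

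Finally, the aim is exploratory and has no stated power, which limits the weight of the point.

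**Conclusion.** The concern holds in a limited form. It is certain from the two lists that all three Aim 3 outcomes are uncollected at this session for anyone above 6 ppm, and that section 9.1 neither declares this restriction nor reconciles it with its ITT rule. It is plausible, but not documented, that selection differs by condition. Any bias is about 0.05 to 0.33 SD under assumed pass rates of 30-50% versus 60-70% and rho of 0.3 to 0.5, smaller if pass rates are high and similar, and zero if pass rates and selection are equal. Its direction rests on the model in the working.

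A reader might extend this to the main result. That is not supported: the primary CPD analysis and the 53 per condition do not use this session. The point merits a change to the plan but does not threaten the trial's main conclusion.

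**What to change.** 1. Add the MNWS, both QSU-brief versions and the purchase tasks to the section 7.8.B list, so that every attendee completes them whatever the CO result.
2. In section 9.1, specify the Aim 3 ANCOVA on all attendees by assigned condition, presented alongside the CO-verified abstinent comparison. Label the latter as conditional on a post-randomisation event and as an explicit exception to ITT.
3. Report the pass rate by condition.
4. Add a sensitivity analysis of the abstinent comparison, adjusted for or weighted on the Week 16 MNWS, QSU and Cigarette Purchase Task values.

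Cost: six further forms (one MNWS, two QSU-brief, three purchase tasks) for people already attending and using REDCap, who are paid $20 for the visit. The all-attendee contrast mixes abstinent and non-abstinent states, in proportions that may differ by condition, which is why both analyses should be shown. Step 1 helps only participants who have not yet reached the session. Steps 2 to 4 need no other new data, although without step 1 the by-assignment analysis in step 2 cannot be run.

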6.2. Measures/Assessments

The following physiological measures will be collected and recorded directly into REDCap by the interviewer:

- 1) CO
- 2) Blood Pressure
- 3) Heart Rate
- 4) Body temperature
- 5) Oxygen saturation
- 6) Respiratory rate
- 7) Urine or Saliva Toxicology
- 8) Urine Pregnancy test (if applicable, to be performed every 2 weeks)

The following assessments will be administered as an interview at Baseline 1 and entered directly into REDCap by the interviewer at the end of the visit:

- 1) Concomitant Medications Form
- 2) Health Changes Questionnaire, which will assess any weekly health changes,
- 3) Time Since Last Cigarette Questionnaire

The following assessments will be administered at Baseline 1 and completed by the participant directly in REDCap:

- 1) BDI
- 2) OASIS
- 3) Respiratory Symptom Questionnaire
- 4) COVID19 Symptom Questionnaire
- 5) Wisconsin Inventory of Smoking Dependence Motives-Brief Scale (WISDM) will be administered to assess nicotine dependence severity.
- 6) Perceived Health Risks Rating¹⁰¹, a measure of the perceived addictive potential and other health risks associated with cigarettes;
- 7) Perceived Stress Scale (PSS)¹⁰¹, assessing the degree to which life situations are perceived as stressful;
- 8) Positive and Negative Affect Scales (PANAS)¹⁰², a measure of changes in positive and negative mood;
- 9) Respiratory Health Questionnaire, a UVM measure of cough, shortness of breath and other respiratory symptoms;
- 10) Minnesota Nicotine Withdrawal Scale (MNWS)¹⁰³, a measure of nicotine withdrawal;
- 11) Questionnaire of Smoking Urges-brief scale - Usual Cigarette (QSU)¹⁰⁴, which measures the urge to smoke;
- 12) Vaping Craving Questionnaire¹⁰⁵, which measures the urge to vape;
- 13) Cigarette Evaluation Scale – Usual Cigarette (CES)¹⁰⁶, which measures responses to cigarettes (e.g., reward, satisfaction);
- 14) Vaping Evaluation Scale (VES), which measures responses to taping (e.g. reward, satisfaction)
- 15) Cigarette Purchase Task – Usual Brand Version (CPT)¹⁰⁷, a self-report analogue of a progressive-ratio schedule that measures the relative reinforcing efficacy of cigarettes by querying how many of that day's cigarette they would consume in a day at varying prices. This task will indicate whether prolonged VLNC cigarette use reduces cigarette demand and increases sensitivity to increases in cigarette costs;
- 16) Snaith-Hamilton Pleasure Scale (SHAPS)¹¹⁰.

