Participants can receive up to \$120.00 for the abstinence session (\$20 if participant does not achieve abstinence, \$120 if participant reaches abstinence), \$40 for biochemical verification of abstinence at 30 day follow up visit, and up to \$306 for completing daily IVR reports of study cigarette and other nicotine and tobacco use. There will also be a \$150 bonus distributed at Week 16 for completing the study. Participants who do not complete the entire study will receive compensation for the sessions that they do complete. Total compensation for completing Study 3, including study visit payments, daily IVR calls and end of study bonus is \$2816. As mentioned above, participants will have a chance to earn additional incentives for compliance, honesty and attendance through urine testing. Participants will be given a debit card at the beginning of the study (during the second portion of the screening visit) and compensation for each visit will be automatically transferred to the card after they complete that visit. If debit cards are unavailable, participants will be paid via an alternate method (i.e. cash or check).

7.10. End of Study:

After a participant has completed all study procedures and has been paid for participation the research assistant will read the following script and give the participant the *Clearing the Air*

Manual.

"If you've reduced your smoking during this study, we encourage you to continue these reductions or even consider quitting. We would like to provide you with some resources should you decide to try to abstain from smoking (give "Clearing the Air" and hotline information). Please also feel free to consult with your physician and use any medications he/she deems appropriate. We will call you in approximately 30 days to ask about your smoking since leaving the study. There is no right answer and we know how difficult quitting can be. Please just answer honestly. The call will take less than 5 minutes. Thanks again for your participation."

The following assessments will be administered using REDCap:

- 1) End of Study Questionnaire

7.11. 30 Day Follow up Phone Call:

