Participants will receive a follow-up phone call between 25 and 35 days after the abstinence assessment session to assess their smoking patterns. The phone questionnaire will last less than five minutes. The questionnaire will ask if the participant is still smoking, how much and whether he/she has attempted to quit smoking since the end of the study. Participants will receive 5 variable incentive program lottery tickets for completing the call as compensation. Those who report abstinence will be invited to complete biochemical verification and be compensated \$40 for doing so. Abstinence will be achieved by a carbon monoxide reading of 6 parts per million (ppm) or under. A urine sample may also be collected to be sent to the lab for analysis. Additionally, any Medical Event Forms that remain open from the last session will be discussed. If the participant became pregnant during the study, this would have been recorded as a medical event. During this phone call, the research assistant will confirm her due date. This event will remain open until delivery. At that time the licensed medical professional will contact the participant to ask a few questions about the baby's health and will update the Medical Event Form.

Once a participant has completed all study procedures and all open events have been closed, the PI or Project Manager will review the participant's record and sign a form indicating study completion for that participant.

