Data will be stored locally at each site. Long-term storage of all study data, for at least 7 years after study completion, will be at the University of Vermont.

12. Adverse Events

The research assistant will ask about adverse events at each session, using a form that assesses the nature, severity, duration, action taken, and outcome of study-related adverse events. AEs will be captured from the time of first study cigarette. Participants will be given contact cards to inform us of events that occur between study contacts. Any AE that remains open will be reviewed and closed at an interview conducted 30 days after the study completion date (completers) or when the study should have ended had the participant completed the study (dropouts and those withdrawn by investigator).

All procedures will be monitored to ensure that they conform to the approved protocol. In addition, monitoring will be done of all unforeseen circumstances that might arise and affect safety; of all reports of serious adverse events as defined in 38 CFR 46 (death, new or prolonged hospitalization, persistent or significant disability/incapacity); of other significant adverse events (adverse events that lead to drop out by the participant or termination by the investigator); of unexpected adverse events resulting from the study, and of expected adverse events.

Any SAE will be brought to the attention of the site PIs as soon as possible and not longer

than 24 hours. Any AE or SAE that is both unexpected and related to study participation will be reported to the IRB within 7 days of the event. The local IRB will make a determination as to whether additional reporting requirements are needed. IRB actions will be reported to the funding agency by the PIs no less than annually and more frequently as recommended by the local IRB. Any SAEs will be summarized in the yearly Progress Reports to the funding agency, including a review of frequency and severity. All SAEs will be followed through ongoing consultation with the physician caring for the patient until they resolve, result in death, or stabilize and are not expected to improve. The study staff will be in close contact with participants and health care providers throughout the study to monitor for potential unanticipated problems. Any unanticipated problems will be discussed at the weekly research staff meetings and reported as required to the local IRB.

13. Withdrawal or Monitoring of Participants

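### As the protocol lists it, nobody actively asks about new adverse events after the abstinence session, 18–30 hours after Week 16; later contacts cover only smoking, events already open and a pregnancy due date

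*Combined protocol and SAP*

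**What the plan says.** **Active questioning.** Section 12 states: "The research assistant will ask about adverse events at each session". It gives a starting point, "AEs will be captured from the time of first study cigarette", but no end point. Section 6.2 introduces a "Health Changes Questionnaire, which will assess any weekly health changes". That form is listed again at every weekly visit (Sections 7.2 and 7.3) and in both branches of the abstinence session (Sections 7.8.A and 7.8.B).

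**Passive route.** Section 12 adds: "Participants will be given contact cards to inform us of events that occur between study contacts".

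**End of product.** Section 8.4 has remaining cigarettes and pods or cartridges collected during Week 16. Section 7.8 places the abstinence session 18–30 hours after the Week 16 visit.

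**Later contacts.** Section 7.11 schedules a call 25–35 days after the abstinence session. On smoking: "The questionnaire will ask if the participant is still smoking, how much and whether he/she has attempted to quit smoking". On health: "any Medical Event Forms that remain open from the last session will be discussed". If a participant became pregnant during the study, the due date is confirmed. Those reporting abstinence are offered biochemical verification. The exit script in Section 7.10 tells participants: "We will call you in approximately 30 days to ask about your smoking since leaving the study". Section 12 describes its own later contact this way: "Any AE that remains open will be reviewed and closed at an interview conducted 30 days after the study completion date". For dropouts and withdrawn participants it ties the equivalent contact to when the study would have ended for them.

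**The concern.** Section 17 lists AEs and serious AEs as safety outcome variables. The participants have affective disorders, and BDI and OASIS are given at every weekly visit and at the abstinence session. That monitoring and the AE questioning both stop about a day after the Week 16 visit. Two of the four arms also lose a supplied nicotine e-cigarette at that point.

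If staff follow the listed call content, a new hospitalization or suicide attempt in the following month enters the safety record only if the participant raises it, in a call announced to them as being about smoking. A low count for that month could not be told apart from a count that is low because nobody asked. With no stated end to AE capture, the two sites could also handle a volunteered event differently.

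**Working it through.** The plan states no figure to reproduce. The check is a comparison of contacts, followed by simple date arithmetic.

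**Contacts side by side**

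| Contact | Listed question about new health events? |
|---|---|
| Weeks 1–16 (Sections 7.2, 7.3) | Yes: Health Changes Questionnaire, Medical Event Form if applicable |
| Abstinence session, either branch (Section 7.8) | Yes: same forms |
| Call at 25–35 days (Section 7.11) | No: smoking, open forms, due date, optional abstinence verification |
| Interview at 30 days (Section 12) | No: open AEs only |

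The Health Changes Questionnaire stands in here for the AE form that Section 12 describes; the protocol does not say they are the same form.

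**Does the call count as a session?** Section 7.11 distinguishes the call from the last session, lists no AE form, and keeps the questionnaire under five minutes. The End of Study Questionnaire in Section 7.10 is not described, but it is given when procedures finish, so it cannot cover the month that follows.

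**Interval for completers**

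- From the abstinence session to the call: 25 to 35 days.
- From the Week 16 visit to the call: 25 days + 18 h = 25.75 days, to 35 days + 30 h = 36.25 days.
- Active questioning covers the first 18–30 h of that, or 0.75–1.25 days.

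**People affected.** Section 9.2 allows 15% loss to follow-up: 212 × 0.85 = 180.2, so about 180 completers. This counts people who have such an interval, not expected events.

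**Dropouts and withdrawn participants.** Active questioning ends at the last attended session. For someone last seen at Week 8 (an illustration), the planned Week 16 is (16 − 8) × 7 = 56 days away. If the 30 days is added, the contact falls at 56 + 30 = 86 days; the Section 12 wording allows either reading.

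**The case against.** The best defence is that this is a coherent design choice. AE capture runs from first study cigarette through the last session, with a later contact to close open events. Contact cards give a route for events between contacts, known serious AEs are followed until they resolve, result in death or stabilize, and staff do speak to participants at about 30 days. All of that stands. None of it is a systematic question about new events.

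The defence is also right about risk. A reader might infer that the protocol itself predicts serious psychiatric harm once product stops. It does not. Section 10.1 expressly ties only mild, transient effects of returning to the usual brand to study end. It describes e-cigarette withdrawal as slightly less severe than cigarette withdrawal, and it presents worsening of depression or anxiety as a rare withdrawal risk during the study. That last risk could also apply when study e-cigarettes stop, but the text does not say so. Nor does it require participants to give up nicotine afterwards.

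A reader might also express the gap as a share of the AE period. That presumes AE capture should run to the call, which Section 12 does not say.

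Finally, the phone form and SOPs are not shown, and some text around the start of Section 14 was not available for this check. A question about new events could exist there. The point is limited to what the protocol text lists.

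**Conclusion.** The gap is real on the text, and its severity is low. For completers, new AEs and serious AEs go without active questioning for 25–35 days after the abstinence session; for dropouts the interval depends on when they were last seen. The documents give no basis for estimating how many events would be missed.

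A reader might infer that the trial's safety comparison or its main results are compromised. The documents do not support that: AEs are asked about at every session while product is supplied, and the Week 16 analyses for Aims 1 and 2 do not use this period. Nor does the text bar recording a later event. It only leaves recording to the participant's initiative.

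The conclusion assumes that the call and the 30-day interview are conducted as Sections 7.11 and 12 describe them, and that product collection coincides with the Week 16 visit, which may be less exact for courier participants.

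**What to change.** At the existing 30-day contact, for completers and for dropouts and withdrawn participants who can be reached:

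- Ask one open question about any new health problem since the last session, and one about any hospitalization.
- Open a Medical Event Form for each new event.
- Refer any suicidality disclosed to a study clinician, or to the Lifeline if none is available. Section 5.5 supplies the contacts, but it is written around screening payment and study withdrawal, so it needs adapting for people who have left the study.
- State in Section 12 that AE collection runs through this contact.

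If the phone form or an SOP already asks about new events, saying so in Sections 7.11 and 12 is enough.

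The cost is a small amendment, a slightly longer call, revised call-length wording in Sections 7.10 and 7.11 and in any matching consent text, and making sure callers know the referral route. No new contact is needed.
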